5.4.2.3 Supplementary analysis

Proportional hazard regression models will be fit for the cause-specific hazard rates of achieving PASI 100 response and permanent discontinuation of IMP independent of pandemic restrictions. The models will be stratified by body weight (≤ 100 kg, > 100 kg) and will include baseline PASI score as a continuous covariate. The estimated cause-specific hazard ratios comparing treatment arms will be presented along with 95% CIs.

THIS DOCUMENT CONTAINS CONFIDENTIAL INFORMATION AND MUST NOT BE COPIED OR MADE AVAILABLE TO ANY THIRD PARTY WITHOUT THE PRIOR WRITTEN CONSENT OF THE LEO PHARMA GROUP

5.4.3 Primary estimand for continuous endpoints

For the primary estimands associated with continuous endpoints, [Panel 17](#) provides an overview of those strategies that are specified in [Panel 2](#) for addressing each of the intercurrent events described in section [5.3](#).

Panel 17. Intercurrent events strategies for primary estimands associated with continuous endpoints

Type of endpoint	Estimand	Strategy for addressing IE		
		Permanent discontinuation of IMP independent of pandemic restrictions	Permanent discontinuation of IMP due to pandemic restrictions	Unblinding of subject
Continuous based on investigator assessments	Primary	‘Treatment-policy’: Occurrences of the IE will be ignored	‘Hypothetical’: Data collected after occurrence of the IE will be excluded. Resulting missing data will be imputed from a multiple imputation algorithm based on the assumption of MAR within treatment arms	‘Treatment-policy’: Occurrences of the IE will be ignored
Continuous based on subject assessments	Primary	‘Treatment-policy’: Occurrences of the IE will be ignored	‘Hypothetical’: Data collected after occurrence of the IE will be excluded. Resulting missing data will be imputed from a multiple imputation algorithm based on the assumption of MAR within treatment arms	‘Hypothetical’: Data collected after occurrence of the IE will be excluded. Resulting missing data will be imputed from a multiple imputation algorithm based on the assumption of MAR within treatment arms

Abbreviations: IE = intercurrent event; IMP = investigational medicinal product; MAR = missing at random.

Again, the strategy for addressing unblinding of subjects will depend on whether the endpoint of interest is based on subject assessments or investigator assessments. This will be elaborated on below.

THIS DOCUMENT CONTAINS CONFIDENTIAL INFORMATION AND MUST NOT BE COPIED OR MADE AVAILABLE TO ANY THIRD PARTY WITHOUT THE PRIOR WRITTEN CONSENT OF THE LEO PHARMA GROUP

Continuous endpoints based on investigator assessments

For ease of explanation, we consider a specific continuous endpoint based on investigator assessments:

- Absolute PASI at Week 16

The primary estimand associated with this endpoint can be seen to assess the LS-mean difference in absolute PASI at Week 16 regardless of permanent discontinuation of IMP and subjects becoming unblinded, if permanent discontinuation of IMP due to pandemic restrictions would not occur. In the following, we elaborate on the estimand strategy described in [Panel 17](#) for this estimand, specifically the ‘hypothetical’ strategy for addressing permanent discontinuation of IMP due to pandemic restrictions.

The hypothetical scenario envisaged is that permanent discontinuation of IMP due to pandemic restrictions would not occur and that subjects who have experienced this event would respond like similar subjects who have not experienced it. Data collected after permanent discontinuation of IMP due to pandemic restrictions will be excluded. The ‘hypothetical’ strategy and the handling of missing data in the main analysis are outlined in [Panel 18](#).

Panel 18. ‘Hypothetical’ strategy for addressing permanent discontinuation of IMP due to pandemic restrictions and handling of missing data in the main analysis of the primary estimand for ‘Absolute PASI at Week 16’

Step no.	Description	Subjects in scope for imputation	Purpose
1	Impute PASI score at Week 16 under MAR assumptions	Subjects who have permanently discontinued IMP due to pandemic restrictions prior to Week 16	‘Hypothetical’ strategy
		Subjects who have not permanently discontinued IMP due to pandemic restrictions prior to Week 16 and whose score at Week 16 is missing	Handling of missing data

Abbreviations: IMP = investigational medicinal product; MAR = missing at random; PASI = Psoriasis Area and Severity Index.

The imputation of PASI scores at Week 16 will be carried out as specified for the primary

THIS DOCUMENT CONTAINS CONFIDENTIAL INFORMATION AND MUST NOT BE COPIED OR MADE AVAILABLE TO ANY THIRD PARTY WITHOUT THE PRIOR WRITTEN CONSENT OF THE LEO PHARMA GROUP

estimand for the primary endpoint. The elaborations above are based on the endpoint ‘Absolute PASI at Week 16’, but the same principles will be applied for the primary estimand associated with other continuous endpoints based on investigator assessments.

Continuous endpoints based on subject assessments

The primary estimand for continuous endpoints based on subject assessments can be seen to assess the LS-mean difference in the continuous endpoint regardless of permanent discontinuation of IMP, if permanent discontinuation of IMP due to pandemic restrictions and unblinding of subjects would not occur. In accordance with [Panel 17](#), this estimand will address unblinding of subjects by the same ‘hypothetical’ strategy as used for addressing permanent discontinuation of IMP due to pandemic restrictions. This means that the above elaboration on estimand strategy also applies to the primary estimand for continuous endpoints based on subject assessments with the exception that unblinding of subjects will be handled just as permanent discontinuation of IMP due to pandemic restrictions.

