14.3.6.4 Estimand strategy for continuous endpoints

Primary estimand for continuous endpoints

For ease of explanation, we consider a specific continuous endpoint based on investigator assessments:

- Absolute PASI at Week 16

The primary estimand associated with this endpoint can be seen to assess the LS-mean difference in absolute PASI at Week 16 regardless of permanent discontinuation of IMP and subjects becoming unblinded, if permanent discontinuation of IMP due to pandemic restrictions would not occur. In the following, we elaborate on the estimand strategy specified in [Panel 21](#) for this estimand, specifically the ‘hypothetical’ strategy for addressing permanent discontinuation of IMP due to pandemic restrictions.

The hypothetical scenario envisaged is that permanent discontinuation of IMP due to pandemic restrictions would not occur and that subjects who have experienced this event would respond like similar subjects who have not experienced it. Data collected after permanent discontinuation of IMP due to pandemic restrictions will be excluded. The ‘hypothetical’ strategy and the handling of missing data in the main analysis are outlined in [Panel 26](#).

THIS DOCUMENT CONTAINS CONFIDENTIAL INFORMATION AND MUST NOT BE COPIED OR MADE AVAILABLE TO ANY THIRD PARTY WITHOUT THE PRIOR WRITTEN CONSENT OF THE LEO PHARMA GROUP

Panel 26 'Hypothetical' strategy for addressing permanent discontinuation of IMP due to pandemic restrictions and handling of missing data in the main analysis of the primary estimand for 'Absolute PASI at Week 16'

Step no.	Description	Subjects in scope for imputation	Purpose
1	Impose PASI score at Week 16 under MAR assumptions	Subjects who have permanently discontinued IMP due to pandemic restrictions prior to Week 16	'Hypothetical' strategy
		Subjects who have not permanently discontinued IMP due to pandemic restrictions prior to Week 16 and whose score at Week 16 is missing	Handling of missing data

Abbreviations: IMP = investigational medicinal product; MAR = missing at random; PASI = Psoriasis Area and Severity Index.

The imputation of PASI scores at Week 16 will be carried out as specified for the primary estimand for the primary endpoint. The elaborations above are based on the endpoint 'Absolute PASI at Week 16', but the same principles will be applied for the primary estimand associated with other continuous endpoints based on investigator assessments.

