In practice, both of these hypothetical questions will be addressed, although in reverse order, by carrying out the steps in [Panel 12](#), each of which will be elaborated on further below. The steps are based on the envisaged hypothetical scenario where permanent discontinuation of IMP due to pandemic restrictions would not occur and subjects who have experienced this event would respond like similar subjects who have not experienced it. In addition to outlining the ‘hypothetical’ strategy for addressing permanent discontinuation of IMP due to pandemic restrictions, [Panel 12](#) specifies the handling of missing data in the main analysis of the primary estimand.

Panel 12. ‘Hypothetical’ strategy for addressing permanent discontinuation of IMP due to pandemic restrictions and handling of missing data in the main analysis of the primary estimand for the primary endpoint

Step no.	Description	Subjects in scope for imputation	Purpose
1	Impute PASI 100 response at Week 16 under MAR assumptions	Subjects who have permanently discontinued IMP due to pandemic restrictions prior to Week 16	‘Hypothetical’ strategy
		Subjects who have not permanently discontinued IMP prior to Week 16 and whose PASI score at Week 16 is missing	Handling of missing data
2	Impute treatment adherence status at Week 16	Subjects who have permanently discontinued IMP due to pandemic restrictions prior to Week 16	‘Hypothetical’ strategy

Abbreviations: IMP = investigational medicinal product; MAR = missing at random; PASI = Psoriasis Area and Severity Index; PASI 100 = 100% improvement from baseline in PASI score.

When performing Step no. 1 in [Panel 12](#), data collected after permanent discontinuation of IMP will be excluded from the imputation models, regardless of the reason for treatment discontinuation. This is well aligned with the ‘composite’ strategy described above for addressing

THIS DOCUMENT CONTAINS CONFIDENTIAL INFORMATION AND MUST NOT BE COPIED OR MADE AVAILABLE TO ANY THIRD PARTY WITHOUT THE PRIOR WRITTEN CONSENT OF THE LEO PHARMA GROUP

permanent discontinuation of IMP independent of pandemic restrictions, where data collected after permanent discontinuation of IMP is irrelevant for the value of the estimand's variable.

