5.5.1 First supplementary estimand

The first supplementary estimand can be seen to assess the difference in response rates achieved regardless of permanent discontinuation of IMP and subjects becoming unblinded, if permanent discontinuation of IMP due to pandemic restrictions would not occur.

In accordance with [Panel 19](#), permanent discontinuation of IMP independent of pandemic restrictions will be addressed using the ‘treatment-policy’ strategy. Specifically, permanent discontinuation of IMP independent of pandemic restrictions will be ignored. The same strategies for addressing permanent discontinuation of IMP due to pandemic restrictions and unblinding of

THIS DOCUMENT CONTAINS CONFIDENTIAL INFORMATION AND MUST NOT BE COPIED OR MADE AVAILABLE TO ANY THIRD PARTY WITHOUT THE PRIOR WRITTEN CONSENT OF THE LEO PHARMA GROUP

subjects will be used, and missing data will be handled in the same way as for the main analysis of the primary estimand, with the exceptions that:

- Data collected from subjects who have permanently discontinued IMP independently of pandemic restrictions prior to Week 16 will be included when performing Step no. 1 of the multiple imputation method.
- Step no. 2 of the multiple imputation method will not be carried out.

These exceptions are introduced to align with the ‘treatment policy’ strategy for addressing permanent discontinuation of IMP independent of pandemic restrictions, which simply ignores treatment discontinuations of that nature. [Panel 20](#) summarises the procedure.

Panel 20. ‘Hypothetical’ strategy for addressing permanent discontinuation of IMP due to pandemic restrictions and handling of missing data in the main analysis of the first supplementary estimand for the primary endpoint

Step no.	Description	Subjects in scope for imputation	Purpose
1	Impute PASI 100 response at Week 16 under MAR assumptions	Subjects who have permanently discontinued IMP due to pandemic restrictions prior to Week 16	‘Hypothetical’ strategy
		Subjects who have not permanently discontinued IMP due to pandemic restrictions prior to Week 16 and whose PASI score at Week 16 is missing	Handling of missing data

Abbreviations: IMP = investigational medicinal product; MAR = missing at random; PASI = Psoriasis Area and Severity Index, PASI 100 = 100% improvement from baseline in PASI score.

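### Continuous endpoints follow a treatment-policy strategy, but missing scores after stopping IMP are imputed from models that leave out all off-treatment data

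*SAP*

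**What the plan says.** For continuous endpoints, SAP 5.4.3 (Panel 17) handles discontinuation of IMP unrelated to pandemic restrictions by a treatment-policy strategy: "Occurrences of the IE will be ignored". The effect on absolute PASI at Week 16 is described as holding "regardless of permanent discontinuation of IMP and subjects becoming unblinded". The section's own exclusion rule is narrow: "Data collected after permanent discontinuation of IMP due to pandemic restrictions will be excluded". Panel 18 then lists who is imputed. Besides pandemic-related discontinuers, these are "Subjects who have not permanently discontinued IMP due to pandemic restrictions prior to Week 16 and whose score at Week 16 is missing".

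For the method, the section refers elsewhere: "The imputation of PASI scores at Week 16 will be carried out as specified for the primary" estimand of the primary endpoint. Protocol 14.3.6.4 has the same sentence: "The imputation of PASI scores at Week 16 will be carried out as specified for the primary estimand for the primary endpoint". Neither adds an exception.

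The specification referred to is in SAP 5.4.1. For Step 1 there, "data collected after permanent discontinuation of IMP will be excluded from the imputation models, regardless of the reason for treatment discontinuation". The reason given is that, under the composite strategy, such data cannot change the value of the variable.

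The first supplementary estimand in SAP 5.5.1 is also treatment-policy for this event. There the SAP states that data from non-pandemic discontinuers "will be included when performing Step no. 1 of the multiple imputation method", and explains that this is done to match the strategy.

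**The concern.** The cross-reference brings a rule written for a composite estimand into a treatment-policy one. Under the composite strategy a subject who stops IMP is a non-responder, so later scores do not matter. For a continuous treatment-policy endpoint the off-treatment score is the quantity wanted.

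The rule also reaches subjects it was not written for. Panel 12, for the primary endpoint, never imputes a non-pandemic discontinuer. Panel 18 does so whenever the score is missing. Read as written, that score is predicted from a model fitted to on-treatment data only. Even the subject's own off-treatment scores are ignored. SAP 5.3 dates discontinuation at the last IMP administration and treats only same-day assessments as preceding it, so an early termination score on a later date is outside the model.

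Week 28 is the most exposed time point. Protocol 10.2.1 lists lack of response after 16 weeks as a reason to stop IMP. Protocol 10.3 asks those stopping at or after Week 16 to attend, at minimum, only an early termination visit. Poor responders may therefore lack Week 28 scores and be imputed from subjects still on drug.

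**Working it through.** The plan states no figure on this point, so the main check is textual.

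| | Primary endpoint (5.4.1) | First supplementary (5.5.1) | Continuous (5.4.3) |
|---|---|---|---|
| Strategy for non-pandemic discontinuation | Composite | Treatment-policy | Treatment-policy |
| Non-pandemic discontinuers imputed if missing? | No (Panel 12) | Yes (Panel 20) | Yes (Panel 18) |
| Their off-treatment data in the imputation model? | No | Yes, by stated exception | No exception stated |

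The last two columns agree in strategy and scope and differ only in the bottom row. The protocol has the same split: the exception is in 14.3.6.2 and absent from 14.3.6.4. The list of changes in SAP Section 6 does not mention it.

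**Size, by assumption.** The documents give no discontinuation rate, no share of discontinuers with missing scores and no off-treatment PASI. Let d be the share stopping, m the share of those with a missing score, and o the off-treatment minus on-treatment mean. If missing scores are drawn at the on-treatment level:

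error in the arm mean = −(d × m × o)

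- d = 10%, m = 50%, o = 4: 0.10 × 0.50 × 4 = 0.20 points too low.
- d = 10%, m = 50%, o = 5: 0.10 × 0.50 × 5 = 0.25 points too low.
- m = 0: no error, whatever d and o.
- Range for d = 5–20%, m = 0–100%, o = 2–6: from 0 to 0.20 × 1.00 × 6 = 1.2 points.

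The error in the treatment difference is the difference between the arms' products. It is zero if d, m and o are equal. With 5% against 15% stopping, m = 50% and o = 5 in both arms, it is (0.15 − 0.05) × 0.50 × 5 = 0.25 points, in favour of the arm with more stopping.

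**Simulation of the remedy.** Two one-arm simulations with d = 10% and m = 50% compared imputation models:

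| Imputation model | Single regression on baseline, o = 4 | Sequential, two preceding visits\* |
|---|---|---|
| On-treatment data only | −0.20 | −0.20 |
| Off-treatment data included, no discontinuation term | −0.19 | −0.16 |
| Separate fit to discontinuers | about 0 | not run |

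\* Stopping at Weeks 6–10, missing after one off-treatment visit, PASI rising 1 point per visit off drug.

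Including the data restores consistency with the estimand but removes only part of the bias, because the model has no term separating subjects on and off drug.

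**The case against.** The strongest reply is that 5.4.3 has its own exclusion rule, limited to pandemic-related discontinuation, and that the cross-reference may mean only the numbered algorithm in 5.4.1. The wider exclusion is tied there to Step 1 of Panel 12, not Panel 18. This reading is possible. It fits poorly with 5.5.1, where the authors thought an explicit exception necessary for the same strategy. At best the text is ambiguous, in a SAP whose introduction says its detail should allow every analysis to be reproduced.

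Second, 5.4.3.2 provides delta-adjusted analyses, and these missing scores would be shifted, by up to 4.5 PASI points at each visit. That is a real partial safeguard. But the margin is the same in both arms, the main estimate is unchanged, and SAP Section 6 drops the retrieved-data analysis that would have used off-treatment scores.

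Third, imputation conditions on the two preceding visits, so a subject who stopped while doing badly is not imputed at the arm average. This is correct and makes d × m × o approximate. Discontinuers are also asked to attend the remaining visits, so m may be small.

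Two inferences should be resisted:

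- A reader might conclude that all off-treatment outcomes are discarded and overwritten, which at d = 10% and o = 4 would double the error to about 0.4. The documents do not support this: the exclusion is from the imputation models, and Panels 17 and 18 keep observed scores in the ANCOVA.
- A reader might take the Section 6 remark that only administrative censoring occurred to mean that no scores are missing. It concerns event times. Discontinuation is a competing event in that model, so withdrawal afterwards would not appear as censoring.

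**Conclusion.** The inconsistency is clear from the text: a stated imputation rule conflicts with the stated estimand, and the plan corrects the same conflict elsewhere. Its effect is confined to missing scores of non-pandemic discontinuers, which are pulled towards on-treatment values. It would go too far to say that the analysis as a whole estimates a had-they-stayed-on-drug effect.

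Confidence is high on the inconsistency and moderate at most on size. The 0.20 to 0.25 points per arm rests wholly on assumed inputs, could be zero, and cancels between arms with equal stopping, missingness and offset. No figure has been worked out for SF-36v2 or the NRS scales.

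The affected analyses lie outside the testing hierarchy and are reported with nominal p-values. The point merits correction but does not threaten the trial's confirmatory conclusions.

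**What to change.** In SAP 5.4.3, directly after the cross-reference, state that:

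1. scores collected after non-pandemic discontinuation of IMP are kept in the analysis and enter the Step 1 imputation models, as in 5.5.1;
2. only data after pandemic-related discontinuation and, for subject-assessed endpoints, after unblinding are left out.

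Where data allow, also include discontinuation status in the imputation model. Section 6 expects too few retrieved data for a separate pattern-mixture model, so a single indicator may be the most that can be fitted; if even that fails, say so and present the main result beside the delta-adjusted ones.

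Record the change in SAP Section 6, since protocol 14.3.6.4 has the same gap. The cost is a few sentences and a small programming change, with no new data.

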5.4.3.1 Main analysis

Each of the 250 imputed datasets will be analysed based on an ANCOVA model, including baseline body weight (≤ 100 kg and > 100 kg), and treatment arm as factors and adjusting for the baseline value of the endpoint as a covariate. The pooled estimate of the difference in the LS-mean between the brodalumab and guselkumab arms, along with the associated 95% CIs and nominal p-values, will be presented based on applying Rubin’s rules to the estimates and standard errors from the aforementioned ANCOVA analyses of the imputed datasets.

5.4.3.2 Sensitivity analyses

Rather than assuming missing data are MAR, the sensitivity analyses will impute missing data based on ‘delta-adjusted’ pattern-mixture models, as described in section [5.4.1.2.1](#).

THIS DOCUMENT CONTAINS CONFIDENTIAL INFORMATION AND MUST NOT BE COPIED OR MADE AVAILABLE TO ANY THIRD PARTY WITHOUT THE PRIOR WRITTEN CONSENT OF THE LEO PHARMA GROUP

5.5 Supplementary estimand analysis

The presentation of supplementary estimands, as defined in [Panel 2](#), will be reserved for the primary endpoint only. For the supplementary estimands, [Panel 19](#) provides an overview of the strategies for addressing each of the intercurrent events described in section [5.3](#).

Panel 19. Intercurrent event strategies for supplementary estimands

Estimand	Strategy for addressing IE		
	Permanent discontinuation of IMP independent of pandemic restrictions	Permanent discontinuation of IMP due to pandemic restrictions	Unblinding of subject
First supplementary	‘Treatment-policy’: Occurrences of the IE will be ignored	‘Hypothetical’: Data collected after occurrence of the IE will be excluded. Resulting missing data will be imputed from a controlled multiple imputation algorithm	‘Treatment-policy’: Occurrences of the IE will be ignored
Second supplementary	‘Composite’: The IE is incorporated as a component in a composite variable with the endpoint of interest	‘Hypothetical’: Data collected after occurrence of the IE will be excluded. Resulting missing data will be imputed from a controlled multiple imputation algorithm	‘Hypothetical’: Data collected after occurrence of the IE will be excluded. Resulting missing data will be imputed from a controlled multiple imputation algorithm

Abbreviations: IE = intercurrent event; IMP = investigational medicinal product.

